8 DATA COLLECTION

8.1 Data Entry

Research staff at sites will enter data onto an eCRF via a secure, web-based portal. Access will be password protected and limited to nominated staff recorded on the delegation log. Members of staff will be identifiable by a unique username and password.

Site staff are responsible for recording full and accurate data onto the database. Anonymised data only will be recorded on trial paperwork and the eCRF. Designated staff at ECTU will follow ECTU SOPs to obtain missing data and resolve queries with site staff and to ensure data quality and completeness of data across sites. Data management will comply with ECTU SOPs TM 06, 07 and 09.

The Data Analysis will be conducted independently of data entry. ECTU statisticians will be responsible for the Data Analysis.

The trial database is a bespoke, ECTU-developed web-interface. Each component of the interface is built and maintained according to ECTU Standard Operating Procedures (ECTU SOPs I.T. 02-09). The trial database includes in-built systems to ensure the validity and quality of the data, and to generate queries. Cross validation will be employed and data entry will be single entry. The trial data will be held on a secure server at Edinburgh Clinical Trials Unit (ECTU), protected by network firewall and antivirus software.

The database servers and file servers are backed up on a daily basis. LTO (linear tape open) and DLT (digital linear tape) tape backup devices with autoloaders write the data to the backup tapes. Specialist software is used to manage the catalogues and automate the scheduled execution of the data backup processes. Full backups occur over the weekend and incremental backups occur during the week. Backup tapes are stored in data grade fire safes capable of withstanding intense temperatures of fire for over two hours. The integrity of backups is tested with sampled restores of data to alternative non-production locations. Data storage media used in the backup processes is controlled and decommissioned appropriately. Network attached storage devices are also used to store replicated copies of large file stores. These devices are protected by strict firewalls.

Data snapshots of databases are stored on access controlled fileservers whenever a statistician performs analysis for data monitoring committees, interim analysis or final analysis. This ensures that their findings can be reproduced. Data that is stored within databases associated with CTIMP studies will have full audit logs enabled so that a history is maintained of who did what and when.

Physical security - Access to the server room is controlled and is limited to essential personnel only.

Logical security 1 - Access to the web-interface will be via the encrypted Secure Socket Layer protocol. Authorisation will be via a unique username/password combination.

Logical Security 2 - Read-only access to the data repository will be provided to analysts on a named basis for a fixed period of time to allow analyses to be undertaken.

8.2 Data transfer

Data transfer where will be covered by agreements. All transfer of data will be in accordance with the Data Protection Act 1998 and the UCL Information Security Policy and Trust Information Governance Policy.

Source Data (in medical notes)	Trial Data (Paper source)	Trial Data (Electronic source)
Medical and MS history Diagnostic investigations Blood results Annotations in notes	Relevant results/observations documented in the notes, transcribed onto source document record (copy to be kept at site)	Details transcribed on source document record inputted onto eCRF held on secure trial website (anonymised electronic data held – ECTU)
Correspondence (e.g. GP letters)		
	Patient questionnaires/trial specific paperwork completed during the trial will form Source Data and be kept at site	Details transcribed on questionnaires/trial specific paperwork inputted onto eCRF (as above)

8.3 Source Data

Data recorded by designated trial staff on the trial specific eCRF will be obtained from the source document, i.e. the medical notes. The source data includes medical and MS history, diagnostic investigations, safety blood results, medical assessments and annotations in the notes. Data completed on paper questionnaires by the trial participants (aided by the research staff) will be source data which is then transcribed onto the CRF (the eCRF held on the secure trial website). As the paper questionnaires are trial specific data, they will be filed in trial specific files. The original paper copy of the questionnaires is source data and will be retained by the site, along with all paper records and trial specific data.

9 STATISTICS AND DATA ANALYSIS

The statistician involved in trial design is [name] (Edinburgh Clinical Trial Unit, University of Edinburgh). Data analysis will be conducted by ECTU statisticians.

9.1 SAMPLE SIZE CALCULATION

9.1.1 Primary MRI Outcome, PBVC

A total of 440 patients will be randomised equally (1:1:1:1) between the three active treatments and the placebo to give 110 per treatment arm. The primary analysis will be intention-to-treat (ITT) on the whole study cohort (n=110/arm). Based on two UK phase II trials (Lamotrigine ⁶⁰ and MS-STAT ²⁷), we expect 10% of the total cohort to drop out of the trial before Year 2, and a further 10% of the total cohort to come for their Year 2 visit, but be off medication. Thus we anticipate 90 patients per arm completing the study.

From the calculations reported in by Altmann et al ⁴³ for measurement of PBVC using the SIENA registration-based method, and further data provided by [name] summarised in the table below (Table A), 90 patients per arm would give over 90% power to detect a 40% reduction in PBVC on any active arm compared to placebo and 80% power to detect a 35% reduction (Bonferroni adjustment for multiple comparisons of three 1.67% two-sided tests, giving 5% overall two-sided significance level). While these sample sizes are based on annual measurement time points and comparison of mean rates of change using longitudinal linear mixed models, Altmann et al also confirm that they are almost identical to the sample size requirements under analysis of covariance of PBVC adjusting for baseline value, the proposed method of analysis in this trial.⁴³

MRI measurement tir	Baseline, 96 weeks						
2-sided significance	0.0167		0.05				
Statistical power		80%	90%	80%	90%		
Treatment effect	30%	123	158	92	123		
	35%	90	116	68	91		
	40%	69	89	52	70		

Table A - Required sample size per arm by treatment effect size, significance level and statistical power; treatment effect expressed as relative mean difference in PBVC under treatment. PBVC assessed using SIENA registration-based method.

For a more exploratory analysis without adjusting for multiple comparisons, this sample size will give almost 90% power to detect a 35% reduction in atrophy. The study is not powered to detect differences between the three active treatment arms.

Notably, sample sizes for using percentage (SIENA) and absolute (SIENAX subtraction) measures of brain volume change have been calculated for a treatment trial in SPMS using data from the placebo arm of a previous trial. The mean/standard deviation ratios of PBVC were much higher than those of absolute BVC after 1 and 2 years of follow up (table 1,⁴³) and the sample size required to show a specified treatment effect were almost 10 times higher when absolute volume change measures were used. Therefore, PBVC is the preferred primary outcome measure for the trial.

9.2 PROPOSED ANALYSES

9.2.1 Recruitment and Baseline

A CONSORT flow diagram will be reported. Exploratory summary methods will be used to describe baseline characteristics: continuous variables will be summarized using summary statistics (mean, standard deviation, median, minimum, and maximum) by treatment group, and categorical variables will be presented using frequency distributions by treatment group. Proportions of patients with missing 96 week MRI data in each treatment group will also be compared, as will baseline data for patients with missing and non-missing 96 week follow-up data.

9.2.2 Primary MRI Outcome Measure

The primary endpoint will be the percentage brain volume change (PBVC) measured using the Structural Image Evaluation, using Normalization, of Atrophy (SIENA) method between baseline and 96 weeks. A normal linear model will be used to compare the three active treatment group arms with placebo adjusting for baseline normalised brain volume and minimisation variables: age, gender, treatment centre (as a fixed effect) and baseline EDSS. The efficacy measure for each active treatment will be the mean difference in PBVC change versus placebo. All patients for whom baseline and 96 week brain volume data are available will be included in the analysis according to the treatment group to which they were randomised irrespective of which treatment(s) they may have received. Dunnett's method will be used to adjust for the multiple pairwise comparisons versus a common placebo group. No formal comparison of the active treatments will be undertaken.

9.2.3 Secondary MRI Outcome

9.2.3.1 Pseudoatrophy:

Using the same methods as for the primary MRI outcome, the mean difference in PBVC from baseline to 6 months between the placebo group and each of the active treatment groups will also be assessed. If the reduction in PBVC is significantly greater in any treatment group a secondary analysis will compare PBVC from week 24 to week 96 between that treatment group and the placebo group using normal linear modelling as in section 9.2.2. As this is an exploratory secondary analysis, no formal adjustment for multiplicity will be made.

9.2.3.2 Counts of new and enlarging T2 lesions:

Each active treatment group will be compared with placebo in terms of the number of new and enlarging T2 lesions between the baseline and 96 week MRI. Over-dispersed Poisson regression models will be used to estimate the percentage difference in new/enlarging lesion count after adjusting for baseline T2 lesion volume and the minimisation variables: age, gender, treatment centre and baseline EDSS.

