2.1.2 Secondary Objectives

- To establish that a multi-arm trial strategy is an efficient way of screening drugs in SPMS and can become the template for future work
- To explore any anti-inflammatory drug activity using the count of new and enlarging T2 lesions

- Examining for evidence of pseudo-atrophy by MRI (to ensure reliability of the primary outcome measure)
- To examine the clinical effect of neuroprotection as measured by clinician (EDSS, MSFC, SDMT, SLCVA, relapse rate) and patient reported outcome measures (MSIS29v2, MSWSv2, Pain [NPRS, BPI and NPS]) and Fatigue [NF])
- To collect basic health economic data (ED-5D) to inform future phase III trials

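### The week 24 to 96 PBVC comparison runs only after a significant week-24 excess loss, a trigger that can miss small-to-moderate pseudo-atrophy

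*Protocol*

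**What the plan says.** Section 2.1.2 lists as a secondary objective "Examining for evidence of pseudo-atrophy by MRI (to ensure reliability of the primary outcome measure"). Section 2.2.2.1 explains why: early loss of non-neuroaxonal volume was seen in an earlier placebo-controlled SPMS trial that also used cerebral atrophy as its primary outcome. The week-24 scan is added for this purpose and is described there as a baseline scan. Section 7.2 (visit 5) schedules it for all patients.

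Section 9.2.3.1 then sets out two steps.

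- Step one has no condition: "the mean difference in PBVC from baseline to 6 months between the placebo group and each of the active treatment groups will also be assessed".
- Step two has one: "If the reduction in PBVC is significantly greater in any treatment group a secondary analysis will compare PBVC from week 24 to week 96", and only between that arm and placebo.

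The section closes: "As this is an exploratory secondary analysis, no formal adjustment for multiplicity will be made". No unconditional week 24 to 96 comparison appears elsewhere in the protocol. The power statement in section 9.1.1 and its Table A concern baseline to 96 weeks only.

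**The concern.** Pseudo-atrophy threatens the 0-96 comparison because early fluid-related loss is subtracted from any real benefit. A comparison from week 24 to week 96 is the natural remedy, since it starts after the early loss has occurred. The protocol collects the data for it on everyone, then releases it only through a significance test.

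That test does not isolate pseudo-atrophy. It sees pseudo-atrophy net of whatever benefit has accrued by week 24. A drug that both protects and causes early volume loss therefore partly hides its own pseudo-atrophy from the trigger. A protective drug could miss on the primary without the protocol producing the estimate that would help to explain the miss.

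There is also a selection effect. When the trigger fires, the 24-96 contrast is shown only for arms chosen on a result that shares the week-24 scan. Scan error that exaggerates loss up to week 24 makes the later change look smaller, so the reported contrast leans towards benefit. The size of this effect has not been quantified.

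**Working it through.** **1. Reproduce the plan's own figure.** With c = SD/mean of 96-week PBVC and r = proportional reduction, n per arm = 2(c·k/r)², where k = z(1−α/2) + z(power). Take the Table A cell r = 35%, α = 0.0167, power 80%, n = 90. Then k = 3.235 and c = 0.35 × √(90/2) / 3.235 = 0.726. With this c, all 12 cells of Table A reproduce within one patient. At 90 per arm the power is 90.4% for a 40% reduction and 80.0% for 35%, which agrees with section 9.1.1 ("90 patients per arm would give over 90% power to detect a 40% reduction in PBVC"). The steps below use c = 0.7275, which gives 90.2% and 79.8%, so the difference is immaterial.

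**2. Inputs.**

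- From the protocol: atrophy of 0.5-1.0% a year (section 1.7.2; 0.5, 0.7 and 1.0 used); a 40% reduction; Dunnett for the primary (section 9.2.2), critical value 2.349.
- n = 110 × 0.9 = 99 per arm. Section 9.1.1 expects 10% drop-out. The further 10% who attend off medication stay in the section 9.2.2 analysis.
- Assumed, because the protocol gives no value: per-scan noise SD e of 0.2, 0.3 or 0.4%; full, constant slowing from day 0; trigger at two-sided 5%.

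**3. What the trigger sees.** At a constant rate, 24/96 = one quarter of the 96-week benefit has accrued by week 24. With one-off early excess loss P, the expected excess loss at week 24 is d24 = P − 0.4 × rate × 24/52. If P is a quarter of the benefit (10% of the placebo 96-week loss), d24 = 0. The trigger then fires 2.5% of the time, whatever the week-24 variance.

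**4. Model.** T = 96/52 years; Var(0-96) = (0.7275 × rate × T)²; slope variance = (Var − 2e²)/T²; week-24 variance = slope variance × (24/52)² + 2e²; SE = SD × √(2/99). The trigger fires with probability Φ(d24/SE24 − 1.96).

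*Worked case: 0.7% a year, e = 0.3, P = half the benefit.*

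- Mean 96-week loss is 0.7 × 1.846 = 1.292%, and Var = (0.7275 × 1.292)² = 0.884.
- Slope variance = (0.884 − 0.18)/3.408 = 0.2065.
- Week-24 SD = √(0.2065 × 0.213 + 0.18) = 0.473, and SE24 = 0.0673.
- d24 = 0.2585 − 0.1292 = 0.129, so the trigger fires Φ(1.92 − 1.96) = 48% of the time.
- Primary: SE relative to the mean = 0.7275 × √(2/99) = 0.1034, so power = Φ(0.20/0.1034 − 2.349) = 34%.

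**5. Results over the range of rates and noise.**

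| Pseudo-atrophy as share of benefit | Primary power | Trigger fires, constant slowing | Trigger fires, no benefit yet at week 24 |
|---|---|---|---|
| 1/4 | 71% | 2.5% | 20-85% |
| 1/3 | 59% | 6-17% | 33-98% |
| 1/2 | 34% | 20-85% | 62-100% |
| 3/4 | 8% | 62-100% | not tabulated |
| all | 1% | 93-100% | not tabulated |

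Without pseudo-atrophy, primary power is 94%. Under constant slowing, an unconditional 24-96 comparison has 87-97% power at two-sided 5%, whatever the pseudo-atrophy. With the protocol's 90 per arm, primary power in the first three rows is 66%, 54% and 31%, and 24-96 power is 84-95%.

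**6. Second check.** A simulation at 90 per arm and 40% slowing kept only trials in which the primary missed and 24-96 would have been significant. Week-24 SD was taken as 0.33 to 0.85 times the 96-week SD. The trigger stayed shut in 91-95% of these trials when pseudo-atrophy was 10% of placebo loss (a quarter of the benefit), 52-83% at 15%, 6-69% at 20%, 0-52% at 25% and 0-7% at 40% (all of the benefit).

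**The case against.** Several points on the other side stand.

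- A reader might infer that the pseudo-atrophy check itself is withheld. It is not. The 0-24 comparison is unconditional for every arm, and with the 0-96 difference it shows roughly how much of any effect arose early. What is missing is a 24-96 estimate with its own interval.
- A reader might also infer that a non-significant week-24 result is to be taken as proof of no pseudo-atrophy. Section 9.2.3.1 says only when a further analysis is triggered, not how a null result is to be read.
- The rule works where the damage is greatest. At three quarters or all of the benefit, when the primary is nearly lost, the trigger usually fires. The lowest figure, 2.5%, belongs to a case in which the primary still has 71% power.
- The offset depends on benefit from day 0. All arms take half dose for the first four weeks (section 6.3) and no onset time is stated. With late onset the trigger fires much more often.
- The analysis is labelled exploratory, and removing the condition would not change the primary test.

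It can also be said that a separate statistical analysis plan may add sensitivity analyses (section 9.2.6). That is weaker, because the protocol itself fixes the trigger.

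One ambiguity works the other way. Section 9.2.3.1 borrows the primary's methods, which include Dunnett, yet ends by disclaiming adjustment. If the trigger is read at the Dunnett level, it fires less often than shown.

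**Conclusion.** The point holds in a limited form. The 24-96 follow-up depends on a test that measures pseudo-atrophy net of early benefit and has no stated power. Under constant 40% slowing it is likely to be withheld when pseudo-atrophy is a quarter to a third of the benefit, where primary power has fallen from 94% to 71% and 59%. At a half, the range of 20-85% does not settle the matter, because it turns on a week-24 variance that the protocol does not give. Beyond that the trigger mostly works.

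The structural defect is certain from the text. Confidence in its size is moderate, since scan noise and onset are assumptions. A reader might go further and infer that a protective drug would be wrongly rejected because of this rule. The documents do not support that: the primary test is the 0-96 comparison with or without the condition, and the 24-96 contrast could only be supportive.

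**What to change.** Delete the condition in section 9.2.3.1. Estimate PBVC from week 24 to week 96 against placebo for all three active arms with the section 9.2.2 model, and report it with confidence intervals beside the 0-24 and 0-96 estimates. Label it supportive, because its baseline is post-randomisation, and say that the primary conclusion rests on 0-96. Reporting every arm also removes the selection on the week-24 result.

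The cost is one more SIENA run per participant (week 24 to week 96) and three model estimates. No new scans or visits are needed.

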9.2.4 Clinical Secondary Outcome Measures

When the change over time in continuous outcomes (EDSS, 9 hole peg test, PASAT, MS functional composite score, Symbol Digit Modalities Test (SDMT), Sloan Low contrast visual acuity (SLCVA), Multiple Sclerosis Impact Scale v2 (MSIS29), Multiple Sclerosis Walking Scale v2 (MSWS), NFI, NPRS, BPI, NPS and health-related quality of life (EQ-5D)) is found to be reasonably normally distributed, perhaps following transformation, these will be compared for active treatments and the placebo groups using normal linear models as in section 9.2.2. If normality cannot be assumed, non-parametric comparison tests will be used. Cox proportional hazard models (adjusting for the minimisation variables) will be used for time to first relapse, timed 25 foot walk and time to progress to a given EDSS score, with the difference between each active treatment and placebo being expressed in terms of a hazard ratio. In exploratory analyses, additional statistical modelling will assess whether composites of imaging and disability measures can be used to predict temporal evolution of SPMS and response to treatment.

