2.2.2.2 Clinical

The current consensus, as codified workshop held in Washington DC in May 2011 and sponsored by the US MS Society and European Committee for Treatment and Research in MS (ECTRIMS), has been published.⁶¹ Whilst recognising the major challenges of measuring disability in a chronic,

Sponsor No.12/0219 v7 Page **27** of **73** unpredictable and multifaceted disease such as MS, it also provides current expert consensus on approaches to MS clinical outcome measurement in trials. We have included outcome measures in MS-SMART that concord with the suggestions and recommendations of the review, namely: (i) expanded disability status scale (EDSS);⁶² (ii) MS Functional Composite scale (MSFC);⁶³ (iii) single digit modality test (SDMT);⁶⁴ (iv) Sloan low contrast visual acuity (SLCVA),⁶⁵ and (v) patient reported outcomes including Multiple Sclerosis Impact Scale (MSIS29v2), ⁶⁶ Multiple Sclerosis Walking Scale (MSWSv2), ⁶⁷ Pain (Numerical Pain Rating Scale [NPRS],⁶⁸Brief Pain Inventory [BPI]),⁶⁹ Neuropathic Pain Scale⁷⁰ and Fatigue (Neurological Fatigue Index [NFI]).⁷¹

The classical measurement tool is the Expanded Disability Status Scale (EDSS),⁶² introduced over 50 years ago, based largely on neurological examination (with some history) and scoring 7 major domains. EDSS is the standard neurological examination tool in assessing MS. The scoring is complex, though as disease severity increases it is largely ambulatory. This trial, like previous SPMS trials will have EDSS entry criteria 4.0 (walking not unrestricted, but >500m) to 6.5 (patients using bilateral assistance to walk), as highlighted below. The EDSS is widely used and supported by the FDA and other regulatory authorities, though is a non-linear ordinal scale and fails to capture cognition in detail. In keeping with previous studies, we will investigate *time to* and *proportion with* confirmed (48 week or 96 week) EDSS progression.

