5.5 RANDOMISATION

5.5.1 Randomisation Procedures

MS-SMART is a double blind trial with additional blinded assessment of secondary and exploratory mechanistic outcome measures. Randomisation will be performed by the research nurse via a secure web-based randomisation service (ECTU) on a 1:1:1:1 basis employing the following minimisation variables:

- sex
- age (<≥ 45yrs)
- baseline EDSS (4.0-5.5; 6.0-6.5)
- site

The minimisation algorithm will incorporate a random element to maintain unpredictability of treatment allocation.

To ensure that treatment allocation remains concealed to both staff and participants, the following measures will be taken:

- Fluoxetine, amiloride and riluzole will be over-encapsulated so they are identical in appearance and the same placebo for fluoxetine, amiloride and riluzole will be used. The fluoxetine/amiloride/riluzole placebo will be identical in appearance in order to disguise the identity
- The same number of the capsules will be prescribed for participants in each arm
- The drugs supplied from the manufacturers will be re-packaged by an organisation independent of the trial and the same organisation will supply pharmacies at participating sites directly with the trial drugs
- Drug supplies to pharmacies will be coded
- The randomisation list will be held by the ECTU to ensure that treatment allocation is concealed from the investigator's team and the participant, whilst providing provisions for emergency un-blinding. Details of the randomisation process will be available in the Investigator Site File (ISF). The identities of the co-ordinating staff whose roles in the trial require them to have access to treatment allocation codes will be recorded in the trial master file (TMF)

The randomisation system will be web-based and require a personal log-in and password. Only those individuals who have attended the site-initiation visit, are trained and are in the delegation-log can carry out this process.

Once a patient has been randomised they will be given a card to indicate they are on the trial with the emergency contact numbers for medical advice. Participants will be instructed to show this card to any healthcare professional involved in their care who is not involved in the trial. Any trial participant who withdraws from the study will not be replaced.
Emergency Un-blinding Procedures

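### Section 9.2.4 does not name each clinical outcome's own baseline as a covariate, and it fixes a normality-driven switch to non-parametric tests with no stated covariates or effect measure

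*Protocol*

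**What the plan says.** Protocol section 9.2.4 lists EDSS, 9HPT, PASAT, MSFC, SDMT, SLCVA, MSIS29, MSWS, NFI, NPRS, BPI, NPS and EQ-5D as continuous outcomes. If change over time in an outcome "is found to be reasonably normally distributed, perhaps following transformation", then "these will be compared for active treatments and the placebo groups using normal linear models as in section 9.2.2". Otherwise: "If normality cannot be assumed, non-parametric comparison tests will be used".

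The model in section 9.2.2 is fitted "adjusting for baseline normalised brain volume and minimisation variables: age, gender, treatment centre (as a fixed effect) and baseline EDSS". Section 9.2.4 names no further covariate for the clinical outcomes.

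In the same section, time to first relapse, the timed 25 foot walk (T25FW) and time to a given EDSS score go to Cox models adjusted for the minimisation variables, with a hazard ratio as the effect measure.

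Section 2.2.2.2 says that EDSS "is a non-linear ordinal scale and fails to capture cognition in detail". Section 9.2.6 leaves to the SAP, among other things, how assumptions will be tested and which sensitivity analyses will be run.

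**The concern.** Two things are fixed badly.

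First, the cross-reference carries over a covariate list built for brain volume. Taken at its word, a model for peg-test time, fatigue or pain would adjust for brain volume and not for the patient's own starting value on that scale. The T25FW model likewise leaves out baseline walking time. The patient's own baseline is usually the strongest available predictor of follow-up. Leaving it out costs precision and leaves chance baseline differences between arms in the estimate.

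Second, the choice of method depends on how the change score is distributed, whereas the linear model's assumption concerns residuals. If the check fails, the replacement has no named test, covariates or effect measure. One outcome could then be reported as an adjusted mean difference and its neighbour by a test of unspecified form, with the split decided after the data are seen. The switch may well be triggered for EDSS, which is listed as continuous here although the protocol itself describes it as ordinal. A phase IIb trial that screens three drugs needs comparable effect estimates on clinical outcomes for planning what follows.

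**Working it through.** **The plan's own figure.** The protocol gives no power or sample size for the clinical secondary outcomes. The nearest figure is Table A in section 9.1.1, for PBVC: 90 per arm for a 35% effect, 80% power and two-sided 0.0167. The table gives no mean or SD, so the mean/SD ratio was solved back from its 12 cells (1.370 to 1.379, average 1.376). Then n = 2(2.393 + 0.842)² / (0.35 × 1.376)² = 20.93 / 0.232 ≈ 90.3, which rounds up to 91 against 90 stated. All 12 cells agree within one patient. This shows only that the table is internally consistent, and nothing in this point disturbs it.

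**Which baselines are in the model.**

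| Outcome | Baseline covariates named | Own baseline named? |
|---|---|---|
| New/enlarging T2 lesions (9.2.3.2) | T2 lesion volume, minimisation variables | Yes, a matching one |
| EDSS change (9.2.4 via 9.2.2) | Brain volume, minimisation variables | Yes, EDSS is one of them |
| The other 12 outcomes (9.2.4 via 9.2.2) | Brain volume, minimisation variables | No |
| T25FW, Cox model (9.2.4) | Minimisation variables | No |

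The schedule in section 7.2 collects all of these clinical baselines at visit 1.

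**Precision.** Let baseline and follow-up have equal variance σ² and correlation ρ. The protocol gives no ρ, so a range is assumed.

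- Variance of the change score: 2σ²(1 − ρ).
- Residual variance after adjusting for own baseline (ANCOVA): σ²(1 − ρ²).
- Ratio of the second to the first: (1 + ρ)/2.
- Extra patients needed without the baseline: 2/(1 + ρ) − 1.

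The last column below takes an effect for which ANCOVA has 80% power at 90 per arm, two-sided 0.05. Power with the change score is then Φ(2.802 × √((1 + ρ)/2) − 1.960).

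| Assumed ρ | Variance ratio | Extra patients | Power with change score |
|---|---|---|---|
| 0.3 | 0.65 | 54% | 62% |
| 0.5 | 0.75 | 33% | 68% |
| 0.7 | 0.85 | 18% | 73% |
| 0.9 | 0.95 | 5% | 78% |

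**Why these are ceiling figures.** The comparator above has no covariates, whereas the planned model has several. Suppose a covariate already in the model correlates r with the outcome's baseline and informs follow-up only through it. The change-score variance falls to σ²[(1 − ρ)²(1 − r²) + 1 − ρ²]. With ρ = 0.5 and an assumed r = 0.5 that is 0.1875 + 0.75 = 0.9375, against 0.75 for ANCOVA, so the cost is 25% and not 33%. If a covariate also predicted follow-up in its own right, ρ would have to be read as the correlation given that covariate.

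**The switch.** If the fallback were a plain rank test on change, its efficiency relative to ANCOVA under normality would be 0.955 × (1 + ρ)/2: 0.72, 0.81 and 0.91 at ρ = 0.5, 0.7 and 0.9. Most of that loss comes from the missing baseline; the rank test itself costs about 5%, and under skew it can gain.

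**The case against.** The best defence is that "using normal linear models as in section 9.2.2" means the same kind of model. Section 9.2.2 pairs PBVC with baseline brain volume, section 9.2.3.2 pairs lesion counts with baseline lesion volume, and section 9.1.1 describes the planned method as covariance analysis on the baseline value. By analogy each clinical outcome would get its own baseline. This stands as a possible reading: own-baseline adjustment is unstated and ambiguous, not excluded.

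A reader might infer more than the text supports:

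- **That no clinical outcome has its baseline in the model.** EDSS does, even on the literal reading.
- **That the fallback is unadjusted and yields only a p-value.** No test is named. A stratified rank test or rank-based covariance analysis, with an estimate beside it, would fit the wording.
- **That normality is judged on pooled data.** The text does not say so, and it allows a transformation first.
- **That raw change scores bias the comparison.** Under randomisation they do not, and regression to the mean acts equally across arms in expectation.
- **That EDSS is handled only as continuous.** There is also a Cox model for time to a given EDSS score, and section 2.2.2.2 adds time to, and proportion with, confirmed progression.

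On T25FW, the event is not defined in section 9.2.4. If it is worsening from baseline, baseline walking time enters through the endpoint, and baseline EDSS carries some walking information. This softens the point without naming the covariate.

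It can also be said that all this is SAP detail. That fails for the switch. Section 9.2.6 leaves open how assumptions are tested, but section 9.2.4 already fixes what follows if normality fails.

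**Conclusion.** The point holds as a matter of precision and clarity for secondary outcomes. Read literally, 12 of the 13 outcomes analysed by linear model lack their own baseline, and the T25FW model names none. The normality switch leads to a method with no stated covariates or effect measure.

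Omitting the own baseline is equivalent to needing about 33%, 18% or 5% more patients at ρ of 0.5, 0.7 or 0.9. These figures assume equal variances at baseline and follow-up, values of ρ that the protocol does not give, and a comparator with no covariates. They are therefore ceilings to the extent that the planned covariates stand in for the missing baseline. At high ρ the loss is small.

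The documents do not support a claim of bias in expectation, and the primary analysis and the sample size are unaffected. The change should be made because it is nearly free, not because the trial's main conclusion is at risk.

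**What to change.** In section 9.2.4 and in the SAP:

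1. State that each outcome's model includes that outcome's own baseline plus the minimisation variables, in place of the bare cross-reference to section 9.2.2.
2. Add baseline T25FW to the T25FW model.
3. Replace the normality switch with one prespecified adjusted analysis for every outcome that gives an estimate and confidence interval: the linear model, with robust or bootstrap intervals if residuals are skewed.
4. Keep rank tests as sensitivity analyses.
5. Optionally, analyse EDSS change with an ordinal model.

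The cost is wording and slightly more analysis work. No new data are needed.
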